7.8 Pregnancy Testing

A serum pregnancy test will be performed at specified visits for female subjects of childbearing potential as defined in Appendix A. Female subjects of reproductive potential should use a highly effective means of contraception (see Appendix A) for the duration of the study and at least 3 weeks after the last dose of abemaciclib

7.9 Investigational Product Compliance

Subjects will maintain a diary documenting adherence to abemaciclib. This diary will be reviewed at the start of each treatment cycle (starting with cycle 2) and at the end of study visit.

7.10 Disease Assessments

7.10.1 Antitumor Effect

For the purpose of this study, patients will be evaluated for response every 8 weeks by CT scan of the chest with or without contrast and triphasic (non-contrast, arterial phase contrast, venous phase contrast) CT scan and/or MRI of the abdomen with IV contrast (pelvis required only if disease documented in pelvis on baseline scan). MRI scans of the abdomen are preferred if the patient is eligible to have this done. The same imaging modality should be used throughout the study.

7.10.2 Definition of Evaluable

Evaluable for toxicity: All patients will be evaluable for toxicity from the time of their first treatment with abemaciclib.

Evaluable for efficacy endpoints, including overall response: Only those patients who have measurable disease present at baseline, have received at least one cycle of therapy (including at least 50% of scheduled abemaciclib doses and at least 1 dose of nivolumab), and have had their disease re-evaluated by appropriate imaging after at least 4 and no more than 12 weeks from cycle 1 day 1 will be considered evaluable for efficacy endpoints including overall response. These patients will have their response classified according to the definitions stated below.

7.10.3 Disease Parameters

CONFIDENTIAL

This material is the property of the University of Pennsylvania.

Measurable disease: Measurable lesions are defined as those that can be accurately measured in at least one dimension (longest diameter to be recorded) as >20 mm by chest x-ray, as >10 mm with CT scan, or >10 mm with calipers by clinical exam. All tumor measurements must be recorded in millimeters (or decimal fractions of centimeters).

Note: Tumor lesions that are situated in a previously irradiated area might or might not be considered measurable.

Malignant lymph nodes: To be considered pathologically enlarged and measurable, a lymph node must be >15 mm in short axis when assessed by CT scan (CT scan slice thickness recommended to be no greater than 5 mm). At baseline and in follow-up, only the short axis will be measured and followed.

Non-measurable disease: All other lesions (or sites of disease), including small lesions (longest diameter <10 mm or pathological lymph nodes with ≥ 10 to <15 mm short axis), are considered non-measurable disease. Bone lesions, leptomeningeal disease, ascites, pleural/pericardial effusions, lymphangitis cutis/pulmonitis, inflammatory breast disease, and abdominal masses (not followed by CT or MRI), are considered as non-measurable.

Note: Cystic lesions that meet the criteria for radiographically defined simple cysts should not be considered as malignant lesions (neither measurable nor non-measurable) since they are, by definition, simple cysts.

'Cystic lesions' thought to represent cystic metastases can be considered as measurable lesions, if they meet the definition of measurability described above. However, if non-cystic lesions are present in the same patient, these are preferred for selection as target lesions.

Target lesions. All measurable and/or evaluable lesions up to a maximum of 2 lesions per organ and 5 lesions in total, representative of all involved organs, should be identified as **target lesions** and recorded and measured at baseline. Target lesions should be selected on the basis of their size (lesions with the longest diameter), be representative of all involved organs, but in addition should be those that lend themselves to reproducible repeated measurements. It may be the case that, on occasion, the largest lesion does not lend itself to reproducible measurement in which circumstance the next largest lesion which can be measured reproducibly should be selected. In subjects who have received locoregional therapy to the liver, lesions that have not been treated locally should be preferentially chosen as target lesions. If a liver lesion that has been treated using locoregional therapy must be chosen as a target lesion, progression of the lesion is required after locoregional therapy. A sum of the diameters (longest for non-nodal lesions, short axis for nodal lesions) for all target lesions will be calculated and reported as the baseline sum diameters. If lymph nodes are to be included in the sum, then only the short axis is added into the sum. The baseline sum diameters will be used as reference to further characterize any objective tumor regression in the measurable dimension of the disease.

Non-target lesions. All other lesions (or sites of disease) including any measurable lesions over and above the 5 target lesions should be identified as **non-target lesions** and should also be recorded at baseline. Measurements of these lesions are not required, but the presence, absence, or in rare cases unequivocal progression of each should be noted throughout follow-up.

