7.10.5 Response Criteria

7.10.5.1 Evaluation of Target Lesions (RECIST 1.1)

Complete Response (CR): Disappearance of all target lesions. Any pathological lymph nodes (whether target or non-target) must have reduction in short axis to <10 mm.

Partial Response (PR): At least a 30% decrease in the sum of the diameters of target lesions, taking as reference the baseline sum diameters

Progressive Disease (PD): At least a 20% increase in the sum of the diameters of target lesions, taking as reference the smallest sum on study (this includes the baseline sum if that is the smallest on study). In addition to the relative increase of 20%, the sum must also demonstrate an absolute increase of at least 5 mm. (Note: the appearance of one or more new lesions is also considered progressions).

Stable Disease (SD): Neither sufficient shrinkage to qualify for PR nor sufficient increase to qualify for PD, taking as reference the smallest sum diameters while on study.

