7.10.5.3 Immune-Related Response in Measurable Lesions (iRECIST)

iRECIST guidelines were established in 2017 to guide response assessments in clinical trials testing immunotherapeutics. Full details of the iRECIST criteria for this study can be found in Seymour L et al, Lancet Oncology 2017 [15].

If initial RECIST 1.1-defined progression (ie, iUPD) is noted on imaging in the setting of clinical stability, subjects may remain on study treatment and have confirmatory imaging in 4-8 weeks (study specified scans every 8 weeks should continue on initial schedule if patient remains on study). An assignment of clinical stability requires that no worsening of performance status has occurred, that no clinically relevant increases in disease-related symptoms such as pain or dyspnea occur that are thought to be associated with disease progression, and that no requirement for intensified management of disease-related symptoms exists, including increased analgesia, radiotherapy, or other palliative care. The imaging findings and the recommendation to continue with treatment despite iUPD should be discussed with the patient before a decision is made about whether or not to continue therapy. Patients who have iUPD and are not clinically stable should be designated as not clinically stable in the case report form. This designation will allow the

CONFIDENTIAL

This material is the property of the University of Pennsylvania.

best overall response to be calculated and the date of iUPD to be used in estimates of progression-free survival.

If radiologic progression is confirmed (iCPD), they will be determined to have progressive disease and discontinued from study therapy, but if repeat imaging shows stable disease or response by RECIST 1.1 they may remain on study therapy with imaging continuing as previously scheduled every 8 weeks (cycle 3 day 1, cycle 5 day 1, etc.).

Table 3: Comparison of RECIST 1.1 and iRECIST

	RECIST 1.1	iRECIST
Definitions of measurable and non-measurable disease; numbers and site of target disease	Measurable lesions are ≥ 10 mm in diameter (≥ 15 mm for nodal lesions); maximum of five lesions (two per organ); all other disease is considered non-target (must be ≥ 10 mm in short axis for nodal disease)	No change from RECIST 1.1; however, new lesions are assessed as per RECIST 1.1 but are recorded separately on the case report form (but not included in the sum of lesions for target lesions identified at baseline)

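### The target-lesion rule in 7.10.3 admits non-measurable lesions to the sum of diameters, against the protocol's own RECIST 1.1 table, so the same scans can give different responses

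*Combined protocol and SAP*

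**What the plan says.** Section 7.10.3, under target lesions, designates "All measurable and/or evaluable lesions up to a maximum of 2 lesions per organ and 5 lesions in total" as targets. A sum of diameters "for all target lesions will be calculated and reported as the baseline sum diameters", so every lesion so designated enters the sum. The same paragraph asks that targets be chosen by size, represent all involved organs and be reproducibly measurable. It does not define an evaluable lesion.

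Earlier in 7.10.3, "small lesions (longest diameter <10 mm or pathological lymph nodes with ≥ 10 to <15 mm short axis), are considered non-measurable disease".

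The RECIST 1.1 column of Table 3 in 7.10.5.3 sets measurable disease at 10 mm or more (nodes 15 mm or more) and then gives: "maximum of five lesions (two per organ); all other disease is considered non-target".

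Section 7.10.5.1 defines partial response (PR) as a fall of at least 30% in the target sum, with no minimum in millimetres. For progression (PD), a 20% rise is not enough: "the sum must also demonstrate an absolute increase of at least 5 mm". Section 7.10.5.4 takes each subject's best response by investigator review, and no confirmatory scan for a response is stated.

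Three places govern who is counted. Section 4.1 item 12 admits subjects with measurable or evaluable disease. Section 7.10.2 requires measurable disease at baseline for the efficacy endpoints. Section 8.4.2, the statistical plan's own efficacy definition, does not repeat that requirement.

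**The concern.** Set beside the word measurable, the word evaluable can only add lesions that are not measurable: those under 10 mm, nodes of 10 to under 15 mm, or other disease that 7.10.3 itself classes as non-measurable. The target-lesion rule therefore contradicts the table that states the RECIST 1.1 rule. The requirement to represent all involved organs gives a reader a reason to pick a small lesion in a second organ.

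The sum decides the primary endpoint. If two investigators follow different parts of the protocol, the same scans can be PR for one and stable disease for the other. When a sum is small, the PR threshold is also only a few millimetres, within reach of reading error. In a trial of 27 subjects, a few such calls could matter.

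**Working it through.** **1. The plan's own figure.** Inputs from 8.3 and 8.4: n = 27, exact one-sided binomial test at 0.10, response rates 18% and 36%. P(X ≥ 7 | 27, 0.18) = 0.200 and P(X ≥ 8 | 27, 0.18) = 0.098, so the rule is at least 8 of 27. Power is P(X ≥ 8 | 27, 0.36) = 0.812, which reproduces the stated 81%. Nothing below changes this.

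**2. The two rules on the same scans.** Lesion sizes are illustrative.

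| Baseline → follow-up | 7.10.3, both lesions in the sum | Table 3, measurable lesion only |
|---|---|---|
| 11 mm → 11 mm; 8 mm → recorded as 0 | 19 → 11, fall 8/19 = 42%: meets PR | 11 → 11, no change: not PR |
| 20 mm → 14 mm; 8 mm → 8 mm | 28 → 22, fall 6/28 = 21%: not PR | 20 → 14, fall 30%: meets PR |

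The disagreement can go either way. An 8 mm lesion recorded as absent gives a fall of at least 30% whenever the rest of the sum is unchanged and no more than 8/0.3 − 8 = 18.7 mm.

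**3. Reading noise when the sum is one small lesion.** The documents give no measurement error, so I assume an independent normal error with SD s of 1, 1.5 or 2 mm per lesion per scan, and no true change. PR requires follow-up ≤ 0.7 × baseline. The quantity follow-up − 0.7 × baseline has mean 0.3L and SD s√(1 + 0.7²) = s√1.49, so

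P(false PR per scan) = Φ(−0.3L / (s√1.49)).

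| Lone lesion | Fall needed for PR | s = 1 | s = 1.5 | s = 2 |
|---|---|---|---|---|
| 9 mm | 2.7 mm | 1.3% | 7.0% | 13.4% |
| 13 mm node | 3.9 mm | 0.07% | 1.7% | 5.5% |
| 30 mm | 9.0 mm | about 0 | about 0 | 0.01% |

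For the 9 mm lesion, PD by size needs a 5 mm rise, against the 2.7 mm fall that suffices for PR. Taking the best of several scans raises these rates: in a simulation of a lone 8 mm lesion at s = 1.5, from 9.5% on one scan to 22.9% on any of three.

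**4. Reading noise when a measurable lesion is also in the sum.** With k lesions summing to S, P = Φ(−0.3S / (s√(1.49k))). At s = 1.5 mm:

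| Measurable lesion alone | With an 8 mm lesion added |
|---|---|
| 11 mm: 3.6% | 1.4% |
| 15 mm: 0.7% | 0.4% |
| 20 mm: 0.05% | 0.06% |

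The added lesion lowers the false-PR rate or leaves it negligible, because the threshold grows with the sum while the noise grows only with √k.

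**5. What a given false-PR rate would do.** If a fraction f of non-responders were scored PR, the null rate would be 0.18 + 0.82f. P(X ≥ 8 of 27) would be 0.120, 0.144 or 0.232 at f = 1%, 2% or 5%. For example, f = 1% would follow if 10% of subjects had small-only sums and 10% of those were false PR. These values of f are illustrations; the documents support no particular one.

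**The case against.** The strongest answer is 7.10.2: a subject without measurable disease is not evaluable for response, so a sum made only of small lesions should never reach the primary analysis. Section 8.4.2 omits the condition but does not say that such subjects count. The choice of targets by size and reproducibility also steers readers to larger lesions. All of this stands and makes the problem narrow. It does not remove the problem, because 4.1 item 12 admits such subjects and 8.4.2 would count them. Section 7.10.2 also asks only that measurable disease be present in the subject; it does not keep non-measurable lesions out of the sum.

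Three stronger readings are tempting and are not supported:

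- A reader might infer that non-measurable lesions generally bias the sum toward response. Step 4 shows that they do not through reading noise, once a measurable lesion is present.
- A reader might take one false responder as given and report that the type I error rises from 0.098 to P(X ≥ 7 | 26, 0.18) = 0.174. That assumes a certain false response, which nothing in the documents establishes.
- A reader might infer that the response rate is no longer comparable with the 18% benchmark. Sections 1.3.1 and 8.3 do not state the response criteria behind the historical rates, so this cannot be judged from the documents.

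**Conclusion.** The contradiction is real and lies in the rule that builds the primary endpoint, so it should be corrected. Its practical reach is limited to two situations: a sum made only of small lesions, and a small lesion recorded as absent beside a small measurable one. The per-scan rates of 1.3% to 13.4% (lone 9 mm lesion) and 0.07% to 5.5% (lone 13 mm node) rest on an assumed reading SD of 1 to 2 mm, independent normal errors and no true change. How many subjects would be affected is unknown, so no overall effect on the type I error can be stated. The design of 8 of 27, with alpha 0.098 and power 0.812, is untouched.

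**What to change.** - In the target-lesion paragraph of 7.10.3, delete *and/or evaluable*, and state that any lesion not meeting the measurable definition is recorded as non-target only, as Table 3 in 7.10.5.3 already provides.
- Carry the measurable-disease condition of 7.10.2 into 8.4.2, and reconcile 4.1 item 12 with it.
- In the same edit, align the cut-offs. Section 7.10.3 calls CT lesions measurable above 10 mm and nodes above 15 mm, while Table 3 includes exactly 10 mm and 15 mm. A lesion of exactly that size is now non-measurable in one place and measurable in the other.

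The cost is wording only: no extra scans or readers, and no change to sample size. Non-measurable lesions are still followed as non-target disease. The small downside is that subjects with only non-measurable disease are then clearly not counted for response and, under 8.4.2, are replaced.

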7.10.4 Methods for Evaluation of Measurable Disease

Clinical lesions: Clinical lesions will only be considered measurable when they are superficial (e.g., skin nodules and palpable lymph nodes) and ≥ 10 mm diameter as assessed using calipers (e.g., skin nodules). In the case of skin lesions, documentation by color photography, including a ruler to estimate the size of the lesion, is recommended.

CONFIDENTIAL

This material is the property of the University of Pennsylvania.

Conventional CT and MRI: This guideline has defined measurability of lesions on CT scan based on the assumption that CT slice thickness is 5 mm or less. If CT scans have slice thickness greater than 5 mm, the minimum size for a measurable lesion should be twice the slice thickness. MRI is also acceptable.

7.10.5 Response Criteria

7.10.5.1 Evaluation of Target Lesions (RECIST 1.1)

Complete Response (CR): Disappearance of all target lesions. Any pathological lymph nodes (whether target or non-target) must have reduction in short axis to <10 mm.

Partial Response (PR): At least a 30% decrease in the sum of the diameters of target lesions, taking as reference the baseline sum diameters

Progressive Disease (PD): At least a 20% increase in the sum of the diameters of target lesions, taking as reference the smallest sum on study (this includes the baseline sum if that is the smallest on study). In addition to the relative increase of 20%, the sum must also demonstrate an absolute increase of at least 5 mm. (Note: the appearance of one or more new lesions is also considered progressions).

Stable Disease (SD): Neither sufficient shrinkage to qualify for PR nor sufficient increase to qualify for PD, taking as reference the smallest sum diameters while on study.

7.10.5.2 Evaluation of Non-Target Lesions

Complete Response (CR): Disappearance of all target lesions. Any pathological lymph nodes (whether target or non-target) must have reduction in short axis to <10 mm.

Partial Response (PR): At least a 30% decrease in the sum of the diameters of target lesions, taking as reference the baseline sum diameters

Progressive Disease (PD): At least a 20% increase in the sum of the diameters of target lesions, taking as reference the smallest sum on study (this includes the baseline sum if that is the smallest on study). In addition to the relative increase of 20%, the sum must also demonstrate an absolute increase of at least 5 mm. (Note: the appearance of one or more new lesions is also considered progressions).

Stable Disease (SD): Neither sufficient shrinkage to qualify for PR nor sufficient increase to qualify for PD, taking as reference the smallest sum diameters while on study.

7.10.5.3 Immune-Related Response in Measurable Lesions (iRECIST)

iRECIST guidelines were established in 2017 to guide response assessments in clinical trials testing immunotherapeutics. Full details of the iRECIST criteria for this study can be found in Seymour L et al, Lancet Oncology 2017 [15].

If initial RECIST 1.1-defined progression (ie, iUPD) is noted on imaging in the setting of clinical stability, subjects may remain on study treatment and have confirmatory imaging in 4-8 weeks (study specified scans every 8 weeks should continue on initial schedule if patient remains on study). An assignment of clinical stability requires that no worsening of performance status has occurred, that no clinically relevant increases in disease-related symptoms such as pain or dyspnea occur that are thought to be associated with disease progression, and that no requirement for intensified management of disease-related symptoms exists, including increased analgesia, radiotherapy, or other palliative care. The imaging findings and the recommendation to continue with treatment despite iUPD should be discussed with the patient before a decision is made about whether or not to continue therapy. Patients who have iUPD and are not clinically stable should be designated as not clinically stable in the case report form. This designation will allow the

CONFIDENTIAL

This material is the property of the University of Pennsylvania.

best overall response to be calculated and the date of iUPD to be used in estimates of progression-free survival.

If radiologic progression is confirmed (iCPD), they will be determined to have progressive disease and discontinued from study therapy, but if repeat imaging shows stable disease or response by RECIST 1.1 they may remain on study therapy with imaging continuing as previously scheduled every 8 weeks (cycle 3 day 1, cycle 5 day 1, etc.).

Table 3: Comparison of RECIST 1.1 and iRECIST

	RECIST 1.1	iRECIST
Definitions of measurable and non-measurable disease; numbers and site of target disease	Measurable lesions are ≥ 10 mm in diameter (≥ 15 mm for nodal lesions); maximum of five lesions (two per organ); all other disease is considered non-target (must be ≥ 10 mm in short axis for nodal disease)	No change from RECIST 1.1; however, new lesions are assessed as per RECIST 1.1 but are recorded separately on the case report form (but not included in the sum of lesions for target lesions identified at baseline)

Target lesions: iUPD; non-target lesions: non-iCR/non-iUPD, or iCR; new lesions: no	iUPD	Remains iUPD unless iCPD is confirmed on the basis of a further increase in sum of measures ≥ 5 mm; otherwise, assignment remains iUPD
Target lesions: iUPD; non-target lesions: iUPD; new lesions: no	iUPD	Remains iUPD unless iCPD is confirmed based on a further increase in previously identified target lesion iUPD in sum of measures > 5 mm or non-target lesion iUPD (previous assessment need not have shown unequivocal progression)
Target lesions: iUPD; non-target lesions: iUPD; new lesions: yes	iUPD	Remains iUPD unless iCPD is confirmed on the basis of a further increase in previously identified target lesion iUPD sum of measures ≥ 5 mm, previously identified non-target lesion iUPD (does not need to be unequivocal), or an increase in the size or number of new lesions previously identified
Target lesions: non-iUPD or progression; non-target lesions: non-iUPD or progression; new lesions: yes	iUPD	Remains iUPD unless iCPD is confirmed on the basis of an increase in the size or number of new lesions previously identified

Target lesions, non-target lesions, and new lesions defined according to RECIST 1.1 principles; if no pseudoprogression occurs, RECIST 1.1 and iRECIST categories for complete response, partial response, and stable disease would be the same.

*Previously identified in assessment immediately before this timepoint. "i" indicates immune responses assigned using iRECIST. iCR=complete response. iPR=partial response. iSD=stable disease. iUPD=unconfirmed progression. non-iCR/non-iUPD=criteria for neither CR nor PD have been met. iCPD=confirmed progression. RECIST=Response Evaluation Criteria in Solid Tumours.

CONFIDENTIAL

This material is the property of the University of Pennsylvania.

